6. RECRUITMENT METHODS

- *Describe the source of potential subjects*
- *Describe the methods that will be used to identify potential subjects*
- *Describe any materials that will be used to recruit subjects. A copy of any advertisements (flyers, radio scripts, etc.) should be submitted along with the protocol.*
- *If monetary compensation is to be offered, this should be indicated in the protocol*

Patients 18 years of age and older with Barrett's esophagus greater than 2cm in length and who are scheduled to undergo an upper endoscopy with VLE exam for surveillance as standard of care will be approached before their scheduled exam to obtain informed consent to participate in this study. No recruitment materials or

advertisements will be used in this study. Subjects will not receive monetary compensation for their participation.

We are fortunate that the two participants of the trial ([name] and [name]) have high volume Barrett's esophagus practices. Both physicians routinely perform VLE. Thus patients who are undergoing VLE as standard of care will be asked if they wish to participate in the trial.

.

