8. NUMBER OF SUBJECTS

- *Indicate the total number of subjects to be accrued locally. If applicable, distinguish between the number of subjects who are expected to be pre-screened, enrolled (consent obtained), randomized and complete the research procedures.*
- *If your study includes different cohorts, include the total number of subjects in each cohort.*
- *If this is multisite study, include total number of subjects across all sites.*

This is a multi-site randomized trial with an anticipated enrollment of 200 patients. We anticipate adding up to 3 other sites. Half of all patients should have a prior diagnosis of dysplasia to ensure a sample that has an adequate number of dysplastic patients.

The primary outcome will be time to interpretation of a VLE scan with and without IRIS. Dysplasia detected in each arm and number of biopsies are secondary outcomes and not expected to be that much different as expert VLE users will be involved in the study. The expected mean time for a VLE without IRIS is 5 min +/- 3 min. The mean time for a VLE without IRIS (standard) is 3 min. With a CI of 95% and power of 90%, the sample size for 1:1 randomization is 94 (47 in each group). Our sample size is 200 to allow for screen failures.

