10. ENDPOINTS

- *Describe the primary and secondary study endpoints*
- *Describe any primary or secondary safety endpoints*

The following outcomes will be measured:

- Primary Outcome: The time for image interpretation in each arm will be compared. Time will be a surrogate for ease of interpretation. Time will be recorded from start of image interpretation to the end of image interpretation. Length of Barrett's will be taken into account (time per cm of Barrett's) when comparing this outcome between patients and procedures.
- Secondary Outcome: Biopsy yield of dysplasia/diagnosis of dysplasia (dysplasia present versus not) of IRIS biopsies (double laser mark) will be compared to VLE without IRIS biopsies (single laser mark) and random biopsies.
- Secondary Outcome: The number of biopsies will be compared among all groups. |

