11. RESEARCH PROCEDURES

- *Include a detailed description of all procedures to be performed on the research subject and the schedule for each procedure.*
- *Include any screening procedures for eligibility and/or baseline diagnostic tests*
- *Include procedures being performed to monitor subjects for safety or minimize risks*
- *Include information about drug washout periods*
- *If drugs or biologics are being administered provide information on dosing and route of administration*
- *Clearly indicate which procedures are only being conducted for research purposes.*
- *If any specimens will be used for this research, explain whether they are being collected specifically for research purposes.*
- *Describe any source records that will be used to collect data about subjects*
- *Indicate the data to be collected, including long term follow-up*

This is a prospective randomized clinical trial examining how IRIS (Intelligent Real-time Image Segmentation) affects biopsy patterns in VLE (Volumetric laser endomicroscopy). Patients will undergo a VLE exam with and without IRIS per the standard of care. All patients regardless of the study participation in this study would receive VLE with and without IRIS clinically. Thus randomization into a particular order will not require more procedure time. They will be randomized into VLE without IRIS first vs VLE with IRIS first. Subjects will be randomized with the BUDDY Randomization System provided for use by the Northwell Health Biostatistics Unit. Randomization will occur before the procedure starts. Randomization will be stratified based on prior diagnosis of dysplasia. The order the patient is randomized to will be recorded on the case report form. There will be concealed allocation as the study coordinator performing the randomization will not know the order of the next allocation.

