12. STATISTICAL ANALYSIS

- *Describe how your data will be used to test the hypotheses.*
- *State clearly what variables will be tested and what statistical tests will be used.*
- *Include sample size calculations.*
- *If this is a pilot study, state which variables will be examined for hypothesis generation in later studies.*

The categorical variables will be compared using Fisher exact tests (eg: presence of dysplasia). Continuous variables between the two groups will be analyzed using the student t-test. All statistical tests will be 2-sided, and $P < .05$ will be considered significant. All statistics will be run using SAS version 9.4 (SAS Institute Inc, Cary, NC, USA).

Time to interpretation is likely normally distributed. For outcomes like number of biopsies, if post study analysis shows this is not normally distributed, we can use median values instead of means or perform a log correction.

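### The planned t-test on interpretation time omits the randomization stratum and the endoscopist, which costs precision but not validity

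*Combined protocol and SAP*

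**What the plan says.** Section 10 makes interpretation time the primary outcome: "The time for image interpretation in each arm will be compared". The one adjustment described is for segment length: "Length of Barrett's will be taken into account (time per cm of Barrett's) when comparing this outcome between patients and procedures". Section 12 names a single method for continuous outcomes: "Continuous variables between the two groups will be analyzed using the student t-test". It adds: "All statistical tests will be 2-sided, and $P < .05$ will be considered significant". Neither section mentions a covariate for stratum, site or reader.

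Section 11 sets the allocation: "Randomization will be stratified based on prior diagnosis of dysplasia". Section 8 wants about half the patients in the prior-dysplasia stratum. No other stratification factor is given. Section 27 gives each site access to the randomization system but does not say that allocation lists are kept by site.

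On who reads the scans, Section 6 describes two participating physicians ("Both physicians routinely perform VLE") and Section 8 says "We anticipate adding up to 3 other sites". The number of endoscopists is never stated. Section 11 also has every patient read under both conditions, with only the order randomized.

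**The concern.** Interpretation time reflects the endoscopist as well as the scan. If endoscopists differ in speed, or if scans from patients with prior dysplasia take longer, that variation stays in the error term of an unadjusted t-test. An analysis that leaves out the factor used to stratify the randomization also gives up the precision that the stratification bought. Because order is not balanced within reader by design, one reader's share of patients can differ between the two groups by chance.

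What is at stake is the width of the interval around the IRIS effect, and whether anyone could see that the result rests on one reader. With two readers of similar volume, each would supply about half the data, and the plan contains no analysis that would show a difference between them.

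**Working it through.** **Inputs.** From Section 8: "The expected mean time for a VLE without IRIS is 5 min +/- 3 min", with the 3 read as a standard deviation; a second mean of 3 min, so a difference of 2 min; 90% power; 47 per group; 200 planned. Section 8 labels both means as being without IRIS. I read them as the two conditions, and that label needs reconciling separately. From Section 12: two-sided 5%. Assumed, because the documents give no figure: the share of variance R² explained by reader and stratum, and the size of any reader or stratum gap.

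**1. The plan's own figure.** n per group = 2 × (1.960 + 1.282)² × 3² / 2² = 47.3. Rounded up this is 48 per group, 96 in total, against the stated 94. The figure reproduces to within 2 patients, as a comparison of two independent groups. Power at 47 per group is 89.8% (normal approximation).

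**2. Removable variance.** Adjusted SD = 3 × √(1 − R²).

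| R² (assumed) | SD, min | n per group for 90% | Power at 47 per group | 95% half-width at 47, min |
|---|---|---|---|---|
| 0 | 3.00 | 47.3 | 89.8% | 1.21 |
| 0.10 | 2.85 | 42.6 | 92.6% | 1.15 |
| 0.20 | 2.68 | 37.8 | 95.1% | 1.09 |
| 0.30 | 2.51 | 33.1 | 97.2% | 1.02 |

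For scale, with 50/50 splits R² = (reader gap² / 4 + stratum gap² / 4) / 9. A 2 min reader gap alone gives 0.11. Gaps of 2 min for both give 0.22. A 3 min reader gap with a 2 min stratum gap gives 0.36.

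**3. If all 200 are evaluable (100 per group).** The unadjusted test has 99.7% power. The half-width is 1.96 × 3 × √(2/100) = 0.83 min; multiplied by √0.9 and √0.7 it becomes 0.79 and 0.70 min.

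**4. Chance imbalance of readers.** With two equal-volume readers (assumed), the difference between groups in one reader's share has SD √(0.25 × 2/47) = 10.3 percentage points, so a 95% range of ±20 points. A 2 min reader gap then moves the estimated difference by up to 2 × 0.20 = 0.40 min. At 100 per group the range is ±14 points and the shift up to 0.28 min.

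**5. Validity.** Simulation: 8,000 trials per cell, 47 per group, two equal-volume readers, order randomized within stratum but not within reader. The adjusted model contains reader and stratum.

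| Reader gap / stratum gap, min | Type I error, t-test | Type I error, adjusted | Power, t-test | Power, adjusted |
|---|---|---|---|---|
| 2 / 0 | 4.9% | 5.0% | 89.3% | 92.2% |
| 2 / 2 | 3.9% | 5.0% | 91.5% | 95.1% |
| 3 / 2 | 4.0% | 5.0% | 92.1% | 97.9% |

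The simulation error on a 5% rate is √(0.05 × 0.95 / 8000) = 0.24 points. A hand check agrees: a 2 min stratum gap contributes variance 2²/4 = 1 of the total 9. Stratified allocation removes that part from the true error, but the t-test still counts it. The effective cut-off is therefore 1.96 × √(9/8) = 2.08, a two-sided error of about 3.8%.

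**6. Within-patient comparison.** If both reads of a patient are compared, and the same endoscopist makes both, reader and stratum main effects drop out of the difference. The number of patients needed is 47.3 × (1 − ρ): 48, 34, 24 and 15 in total at within-patient correlations ρ of 0, 0.3, 0.5 and 0.7 (assumed, with equal SDs and no order effect).

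**The case against.** The strongest reply is that nothing is broken. Order is randomized per patient, so chance differences in reader mix are part of what the t-test's standard error measures. Prior dysplasia is balanced by design. On the plan's own inputs 200 patients give ample power, so a smaller required number saves nothing. This all stands. A reader might infer that endoscopist is confounded with group, that the false-positive rate is raised, or that the trial is underpowered. The documents support none of these: simulated type I error is nominal or below, and power is about 90% even at 47 per group.

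A second reply is that the point matters less than the unsettled choice between a between-patient and a within-patient comparison. That also stands. The t-test wording and the 47-per-group calculation imply independent groups, while Section 11 collects both reads on everyone. In a within-patient analysis the main effects discussed here largely cancel. The choice must come first, because no single list of terms serves both. On first reads, read order is either constant or indistinguishable from IRIS on/off. On both reads, a model without a patient term treats two correlated times as independent.

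Third, the sizes rest on assumptions. The documents do not show that readers differ in speed. The calculation is also in raw minutes, whereas Section 10 intends time per cm, on which scale the shares could differ.

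What survives is that no stratum or reader term, and no result by reader, is planned, and that adding them costs almost nothing.

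**Conclusion.** The point holds as a matter of efficiency and interpretability. With stratum and reader together explaining an assumed 10% to 30% of the variance, the interval at 47 per group narrows by 5% to 16% (1.21 to 1.15 or 1.02 min). With all 200 evaluable the proportional narrowing is the same and power is not an issue in either analysis. The mild conservatism of the t-test depends on the stratum being prognostic for time.

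These figures apply to a between-patient comparison of first reads. In a within-patient comparison the gain from reader and stratum terms largely disappears, and the check by reader is what remains. That the readers are few is an inference from two physicians and up to three added sites.

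**What to change.** In Section 12, state which comparison is primary and fit the model that matches it.

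- **Between patients, first reads only:** a linear model with IRIS on/off, prior-dysplasia stratum and endoscopist as a fixed effect, and no read-order term.
- **Both reads per patient:** a model with patient (random or fixed), IRIS on/off and period.

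In either case, report the IRIS effect separately by endoscopist as a descriptive check, noting that small reader subgroups will be imprecise. With so few readers as fixed effects, the result speaks for these readers. Confirm that the case report form records the endoscopist, since the list of recorded data in Section 14 does not name that item.

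The cost is a few lines of text. In the first-read model it also takes a few degrees of freedom: one for the stratum and one fewer than the number of endoscopists. No new patients, procedures or randomization strata are needed. Fixing the terms now also prevents covariates being chosen after the data are seen.

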13. SPECIMEN BANKING

- *If specimens will be banked for future research, describe where the specimens will be stored, how long they will be stored, how they will be accessed and who will have access to the specimens*
- *List the information that will be stored with each specimen, including how specimens are labeled/coded*
- *Describe the procedures to release the specimens, including: the process to request release, approvals required for release, who can obtain the specimens, and the information to be provided with the specimens.*

[N/A]

14. DATA MANAGEMENT AND CONFIDENTIALITY

- *Describe the data and specimens to be sent out or received. As applicable, describe:*

- *What information will be included in that data or associated with the specimens?*
- *Where and how data and specimens will be stored?*
- *How long the data will be stored?*
- *Who will have access to the data?*
- *Who is responsible for receipt or transmission of data and specimens?*
- *Describe the steps that will be taken to secure the data during storage, use and transmission.*

Data being collected for this study will adhere to the institutional policies related to research. Data related to the procedure and device will be recorded, including date of procedure, indication for procedure, concurrent medications. Medical history will also be recorded, including previous histopathological diagnoses, previous medications, and previous therapy for Barrett's esophagus. The data will be stored on Northwell's REDCap server. |

15. DATA AND SAFETY MONITORING PLAN

A specific data and safety monitoring plan is only required for greater than minimal risk research. For guidance on creating this plan, please see the [Guidance Document on the HRPP website](#).

Part I – this part should be completed for all studies that require a DSMP.

Part II – This part should be completed when your study needs a Data and Safety Monitoring Board or Committee (DSMB/C) as part of your Data and Safety Monitoring Plan.

Part I: Elements of the Data and Safety Monitoring Plan

- *Indicate who will perform the data and safety monitoring for this study.*
- *Justify your choice of monitor, in terms of assessed risk to the research subject's health and well being. In studies where the monitor is independent of the study staff, indicate the individual's credentials, relationship to the PI, and rationale for selection*
- *List the specific items that will be monitored for safety (e.g. adverse events, protocol compliance, etc)*
- *Indicate the frequency at which accumulated safety and data information (items listed in # above) will be reviewed by the monitor (s) or the DSMB/C.*
- *Where applicable, describe rules which will guide interruption or alteration of the study design.*
- *Where applicable, indicate dose selection procedures that will be used to minimize toxicity.*
- *Should a temporary or permanent suspension of your study occur, in addition to the IRB, indicate to whom will you report the occurrence.*

Data will be closely monitored by the PI. This monitoring will be done on an ongoing basis and will focus on any adverse events or unanticipated problems which will be reported immediately to the PI. These will be analyzed for relatedness, although no relatedness to research is anticipated since this is data collection only. Protocol compliance will be monitored via data entry in REDCap and by verification of source documentation when required. |

Part II: Data and Safety Monitoring Board or Committee

- *When appropriate, attach a description of the DSMB.*
- *Provide the number of members and area of professional expertise.*
- *Provide confirmation that the members of the board are all independent of the study.*

N/A

16. WITHDRAWAL OF SUBJECTS

- *Describe anticipated circumstances under which subjects will be withdrawn from the research without their consent*
- *Describe procedures for orderly termination*
- *Describe procedures that will be followed when subjects withdraw from the research, including partial withdrawal from procedures with continued data collection.*

If the subject consents to the study and meets all criteria at the time of the initial procedure, they will be considered enrolled unless the patient provides written documentation of their decision to withdraw from the study. |

17. RISKS TO SUBJECTS

- *Describe any potential risks and discomforts to the subject (physical, psychological, social, legal, or other) and assess their likelihood and seriousness and whether side effects are reversible. Where appropriate, describe alternative treatments and procedures that might be advantageous to the subjects.*
- *Include risks to others , like sexual partners (if appropriate)*
- *Discuss why the risks to subjects are reasonable in relation to the anticipated benefits and in relation to the importance of the knowledge that may reasonably be expected to results*

- *Describe the procedures for protecting against or minimizing any potential risks, including risks to confidentiality, and assess their likely effectiveness.*

There are no additional risks or discomforts anticipated for the patient if he or she decides to participate in this research. Subjects' alternatives are to not participate in the research study. |

18. RESEARCH RELATED HARM/INJURY

- *Describe the availability of medical or psychological resources that subjects might need as a result of anticipated problems that may be known to be associated with the research.*
- *If the research is greater than minimal risk, explain any medical treatments that are available if research-related injury occurs, who will provide it, what will be provided, and who will pay for it.*

Subjects will be undergoing VLE with and without computer enhancement as part of their standard of care. They are aware of and consent to this procedure and associate risks separately from this research study. The research component will involve recording information during the exam. It is not anticipated that this causes any additional risk. De-identified data will be recorded in an encrypted database. While there is always a potential for breach of information, every effort is in place to ensure this security. |

19. POTENTIAL BENEFIT TO SUBJECTS

- *Explain what benefits might be derived from participation in the study, noting in particular the benefit over standard treatment (e.g. a once-a-day administration instead of four times a day, an oral formulation over an IV administration).*
- *Also state if there are no known benefits to subjects, but detail the value of knowledge to be gained*

While this research will likely not provide subjects' any direct benefit, it will potentially benefit patients with the same disease in the future. |

20. PROVISIONS TO PROTECT PRIVACY INTERESTS OF SUBJECTS

- *Describe the methods used to identify potential research subjects, obtain consent and gather information about subjects to ensure that their privacy is not invaded.*
- *In addition consider privacy protections that may be needed due to communications with subjects (such as phone messages or mail).*

Research related documents used to record information for this study, such as data stored on paper (informed consent forms, case report forms, procedure reports, pathology reports) will be stored in locked cabinets which are only accessible to those approved to participate in this study. Electronic information will be kept within the HIPAA compliant database, REDCap. Any email correspondence with potentially-identifying information will be encrypted. |

21. COSTS TO SUBJECTS

- *Describe any foreseeable costs that subjects may incur through participation in the research*
- *Indicate whether research procedures will be billed to insurance or paid for by the research study.*

There are no additional costs to subjects if they choose to participate in this study. |

22. PAYMENT TO SUBJECTS

- *Describe the amount of payment to subjects, in what form payment will be received and the timing of the payments.*

Subjects will not be paid for participating in this study. |

23. CONSENT PROCESS

If obtaining consent for this study, describe:

- *Who will be obtaining consent*
- *Where consent will be obtained*
- *Any waiting period available between informing the prospective participant and obtaining consent*

- *Steps that will be taken to assure the participants' understanding*
- *Any tools that will be utilized during the consent process*
- *Information about how the consent will be documented in writing. If using a standard consent form, indicate such.*
- *Procedures for maintaining informed consent.*

Consent for this study will only be obtained by those approved to do so. At the time of consent, the investigator will explain in detail the data that will be collected as part of this study. It will be explained to subjects why they are eligible to participate. Before signing the consent form, patients will be asked if they understand what their participation involves. Original copies of the consent forms will be stored in a study binder accessible to the research staff. Subjects will be given a copy of the signed consent form for their records. The subject, investigator, and a witness will print and sign their names and the date the informed consent process takes place. Enrollment notes will be written to outline the process and these will be signed by the investigator.]

In the state of NY, any participants under the age of 18 are considered children. If your study involves children, additional information should be provided to describe:

- *How parental permission will be obtained*
- *From how many parents will parental permission be obtained*
- *Whether permission will be obtained from individuals other than parents, and if so, who will be allowed to provide permission. The process used to determine these individual's authority to consent for the child should be provided*
- *Whether or not assent will be obtained from the child*
- *How will assent be documented*
- *Whether child subjects may be expected to attain legal age to consent to the procedures for research prior to the completion of their participation in the research. If so, describe the process that will be used to obtain their legal consent to continue participation in the study. Indicate what will occur if consent is not obtained from the now-adult subjects.*

N/A

If the study involves cognitively impaired adults, additional information should be provided to describe:

- *The process to determine whether an individual is capable of consent*
- *Indicate who will make this assessment*

- *The plan should indicate that documentation of the determination and assessment will be placed in the medical record, when applicable, in addition to the research record.*
- *If permission of a legally authorized representative will be obtained,*
 - *list the individuals from who permission will be obtained in order of priority*
 - *Describe the process for assent of subjects; indicate whether assent will be required of all, some or none of the subjects. If some, which subjects will be required to assent and which will not.*
 - *If assent will not be obtained from some or all subjects, provide an explanation as to why not*
 - *Describe whether assent will be documented and the process to document assent*
 - *Indicate if the subject could regain capacity and at what point you would obtain their consent for continued participation in the study*

N/A

If the study will enroll non-English speaking subjects:

- *Indicate what language(s) other than English are understood by prospective subjects or representatives*
- *Indicate whether or not consent forms will be translated into a language other than English*
- *Describe the process to ensure that the oral and written information provided to those subjects will be in that language*
- *If non-English speaking subjects will be excluded, provide a justification for doing so*

N/A

